#### 6. SAFETY

In spite of all reasonable precautions, there is small potential anticipated risk, that participants may feel uncomfortable in sharing personal feelings about not following their medication regimen.

If phases one or two reveal medication practices that comprise a real and present risk to the patients' health and safety, this will be discussed with the study pharmacist and cardiac consultant, as indicated. The researcher will obtain patients' agreement that they seek further information and help from their General Practitioner (GP) if the study reveals they have problems related to how they take their heart medications and they remain unable or unwilling to take them as prescribed despite the intervention.

#### 7. BLINDING AND UNBLINDING

Neither participants nor researcher can be blinded to the group allocation of participants (intervention or usual care only groups).

#### 8. STATISTICAL CONSIDERATIONS

#### Sample Size or Power Calculation

Sample size for the RCT was calculated based on data from Ma et al. (2014). The researcher predefined and utilised the value for the means (M) and standard deviation (SD) based on Ma et al. using the following formula:

Cohen's 
$$d = M_1 - M_2 / \sigma_{\text{pooled}}$$
, where  $\sigma_{\text{pooled}} = \sqrt{[(\sigma_1^2 + \sigma_2^2) / 2]}$   
 $r_{Y\lambda} = d / \rightarrow square\ root\ (d^2 + 4)$ 

M1= means for group  $1 = 29.72 \pm 3.46$ 

M2= means for group  $2 = 25.30 \pm 3.11$ 

The resultant value for 2 sided test for alpha = 0.05, with power = 0.80, is a sample size of 9 for each group. The formula for calculation of the sample size is set out in Box 1 and for this study produced:

n= 
$$2[(a+b)^2\sigma^2)$$
]  
 $(\mu_1-\mu_2)^2$ 

$$n=2[(1.96+0.842)^2 3.285^2)]$$

$$(29.72-25.3)^2$$

$$N = 2[(2.802)^{2} 3.285^{2})]$$
 =  $2[7.8512 \times 10.7912]$  =  $2[84.7239]$  =  $169.448 = 8.67$   
19.5364 19.5364 19.5364 19.5364

9 participants per group.

Box 1: Formula for a continuous outcome and equal sample sizes in both groups, assuming: alpha = 0.05 and power = 0.80 (beta = 0.20)

n= the sample size in each of the groups  $\mu_1=$  population mean in treatment Group 1  $\mu_2=$  population mean in treatment Group 2  $\mu_1-\mu_2=$  the difference the investigator wishes to detect  $\sigma^2=$  population variance (SD) a= conventional multiplier for alpha = 0.05 b= conventional multiplier for power = 0.80  $\frac{n=2\left[(a+b)^2\sigma^2\right]}{\left(\mu_1-\mu_2\right)^2}$ 

Allowing for 50% loss to follow-up, based on these calculations, a sample size of 28 participants for both groups will be needed in the pilot trial phase to ensure an adequate response rate for statistical analysis.

#### 9. STATISTICAL ANALYSIS PLAN

**Phase one:** Questionnaire data will be analysed using descriptive statistics to illustrate the patients' baseline characteristics. Data will be entered into an Excel spread sheet, checked and cleaned prior to being entered into SPSS for Windows version 23. The mean will be used to assess the values of medication adherence, medication adherence self-efficacy, and beliefs about medication. The amount of variation or dispersion of data values will be quantified using standard deviation (SD) to demonstrate how close these values lie from their Means. Bivariate analyses will be conducted, examining factors potentially associated with medication non-adherence.

Version 2: 20/05/2016 ----- Page 21 of 42

Logistic regression will be used to investigate factors and behaviours predictive of medications non-adherence. Two sided p values less than .05 will be considered to indicate statistical significance.

**Phase two:** Data collection and analysis will be conducted simultaneously to build on emerging themes (Polit and Beck, 2014). An inductive approach will be applied to the data, based on thematic analysis to analyse interview transcripts (Sim, 1998). This approach will focus on identifying, analysing and reporting recurrent patterns (themes) and subcategories within the data (Liamputtong, 2013). This method will examine and compare data to identify similarities and differences by reading carefully through each transcript and searching across the data set (Liamputtong, 2013, Polit and Beck, 2014). The coding process will use QSR NVivo to analyse interviews data. Thematic analysis will be conducted in six steps (Braun and Clarke, 2006).

- **1. Familiarity with the data**: Transcribing the verbal data into written format entails close and extensive reading and inserting notes into transcribed material where appropriate.
- **2. Generated codes**: Creating codes will arrange the data into meaningful groups.
- **3. Searching for themes:** All relevant coded data will be extracted and grouped into initial subthemes. Main themes covering sub-themes will be developed in order to address the research questions.
- **4. Reviewing themes**: When all themes and sub-themes are entered, the next step is to look for common categories or themes across the entries for each question to form a coherent pattern. If some entries seem inconsistent for their category, the candidate themes will be re-categorised to find themes that adequately capture the contours of coded data. Next, the full data set is re-read to examine data relative to the themes, coding any supplementary data within themes if not coded in the first stage.
- **5. Defining and naming themes**: After categorising and organising the data and themes, themes will be further determined and refined by defined titles that capture the full sense and essence of each single theme (Braun and Clarke, 2006).
- **6. Writing a report**: Once interview findings are organised in the synthesised format or thematic map, they will be ready for presentation. Ultimately, the researcher will write a report including data extracts to provide a concise, coherent, logical, non-repetitive and interesting account of the

Version 2: 20/05/2016 ----- Page 22 of 42

story the data tell within and across themes. Next, these extracts will be embedded within an analytic narrative that needs to go beyond description of the data to compellingly illustrate the research questions and their relationship to the argument and whether the argument has been completely answered. The study questions will be addressed by analysing the finding from quantitative phase to inform qualitative findings by developing an interpretation to merge the data and find the relationship between the quantitative results and the qualitative argument.

**7.** In the short term data that will emerge from qualitative analysis can reveal critical insights to inform development, translation, and dissemination of interventions to improve medication adherence behaviours.

If the researcher finds any contradiction between survey and interview responses, the participant will be asked to consider their responses and confirm which answer to take into account to ascertain if the patients is eligible for the trial phase.

Pilot trial phase: The researcher will compare the two groups at baseline. Data will be analysed according to intention to treat analysis using statistical methods based on the study hypothesis. The primary outcome will be medication adherence/non-adherence at six months and changes in adherence scores since baseline. Descriptive statistical analyses will be used to illustrate the participants' baseline characteristics. The independent samples t-test will be used to compare the mean medication adherence questionnaire scores (MSSS, MAQ, ARMS, BaMQ, and MASER-R) between the intervention and usual care groups. Paired samples t-test analysis will be used to test within groups differences on medication adherence questionnaire scores (MSSS, MAQ, ARMS, BaMQ, and MASER-R). Logistic regression analysis will be applied to identify variables that significantly influence adherence to medications (i.e. self-efficacy, beliefs, level of confidence, and social support).

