#### 2. STUDY OBJECTIVES

#### 2.1. PRIMARY OBJECTIVES (PHASE 1 AND 2) AND OUTCOMES

- 1. To determine self-reported adherence or non-adherence to prescribed cardiac medications in cardiac patient referred to a cardiac rehabilitation program. The outcome will be self-reported medication adherence/non-adherence.
- To explore individual, behavioural and environmental factors that affect adherence to cardiac medications. The outcome will be identification of factors that influence adherence to medications.

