Non-adherence to medications will be assessed by the **Medication Adherence Questionnaire** (**MAQ**) designed to measure medication adherence behaviour and barriers such as forgetfulness, carelessness, adverse effects and efficacy. MAQ includes simple four-item dichotomous questions, scoring one point for each yes response; total scores are categorised as: 0 point indicating high; 1-2 points medium, and 3-4 points low medication adherence behaviour.

The Adherence to Refills and Medications Scale (ARMS) will be used to determine the patient medication adherence behaviour in terms of self-regulation. The ARMS comprises a 12-item scale with the first 8-item medication taking subscale assessing correct self-administration ability for the prescribed regimen. The next 4-item prescription refill subscale assesses the patient's ability to refill medications on schedule. Each item is scored on a four point scale ranging from l=

Version 2: 20/05/2016 ----- Page 15 of 42

none of the time to 4= all the time. The higher numbers on the scale demonstrate patient's better ability to refill medications on schedule.

The Belief about Medicine Questionnaire (BaMQ) elicits information on patients' beliefs about their medicines where they may relate to adherence. It identifies whether the patient holds beliefs that their medicines are necessary or if they have concerns about their medicines. The study will use the short version of the BaMQ (the 8-item) developed by Horne et al., 1999. This version is composed of four subscales containing two items each, and assessing: General Harm; General Overuse; Specific Necessity; and Specific Concerns. Respondents indicate their degree of agreement with each statement on a five point Likert scale, ranging from l=strongly disagree to 5=strongly agree. The lower numbers on the scale demonstrate the patient's strong beliefs about taking medications. Scores are summed to give a total score, with higher scores indicating more positive beliefs. The focus of the BaMQ, is identification of barriers to medication adherence, contributing to comprehensive evaluation of the drivers behind medication adherence.

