#### 5.4. RECRUITMENT AND SCREENING

Patients identified as 'non-adherent' to at least one of their cardiac medications based on the result of exploratory phases (Phase One and Phase Two) will be invited to participate in this pilot

Version 2: 20/05/2016 ----- Page 18 of 42

randomised trial phase. Participants will be assessed as adherent or non-adherent based on the response to the Medication Adherence Questionnaire (MAQ). Patient with a total score of 1-2 will be considered as "adherent", and those with a total score of 3-4 as "non-adherent". At conclusion of the interview (Phase Two), eligible participants who are identified as "non-adherent" will be informed about Phase 3, the pilot RCT trial phase.

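### Phase one plans a binary logistic regression to find factors linked to non-adherence; if the outcome is the MAQ 3-4 cut, ordered information is lost, at an illustrative cost of about 7 to 16 power points

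*Protocol*

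**What the plan says.** Section 2.1 makes the search for associated factors a primary objective: "To explore individual, behavioural and environmental factors that affect adherence to cardiac medications". For the quantitative part, section 9 (Phase one) names the model, "Logistic regression will be used to investigate factors and behaviours predictive of medications non-adherence", and the test level, "Two sided p values less than .05 will be considered to indicate statistical significance". It also plans means and standard deviations of the scores, and less specifically: "Bivariate analyses will be conducted, examining factors potentially associated with medication non-adherence".

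Section 9 does not say how non-adherence is coded in the regression. That has to be read from two other places:

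- Section 5.3.1 makes the MAQ the measure of non-adherence. It has four yes/no items, one point per yes, and three ordered bands: "0 point indicating high; 1-2 points medium, and 3-4 points low medication adherence behaviour".
- Section 5.4, on recruitment and screening, gives the only two-way split: "Patient with a total score of 1-2 will be considered as 'adherent', and those with a total score of 3-4 as 'non-adherent". A score of 0, the best adherence, is in neither class.

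**The concern.** A logistic regression needs a yes/no outcome, while the MAQ gives an ordered score from 0 to 4. With the section 5.4 split as outcome, a patient scoring 0 (once placed) counts the same as one scoring 2, and a 3 the same as a 4. The split is needed to decide who is offered the trial. Nothing in the protocol requires it for studying which factors go with poorer adherence, and section 9 elsewhere uses the graded score, as means in Phase one and in t-tests in the pilot trial.

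At stake is the chance of detecting real associations with beliefs, self-efficacy and social support. The survey cannot simply be enlarged to compensate: section 3.3 ties its size to filling the pilot trial, and section 3.5 puts patient flow at about 29 a month.

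**Working it through.** **The plan's own figure.** The only sample size calculation is for the pilot trial: 2 × 2.802² × 3.285² / 4.42² = 8.67, so 9 per group. It reproduces, but says nothing about Phase one. No sample size, effect size, MAQ distribution or power is stated for the Phase one regression.

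**Inputs from the protocol**
- Two-sided alpha 0.05 (section 9).
- Non-adherence of 33% to more than 50% in cardiac patients (section 1.1). This is background literature, not a figure for MAQ 3-4.
- 28 trial participants (section 3.3) and about 29 attenders a month for six months (section 3.5).

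**Assumptions**
- Survey size: 28/0.50 = 56 or 28/0.33 = 85 if every non-adherent patient joins the trial; the ceiling is 6 × 29 = 174. With 50% non-adherent, N = 85 corresponds to 28/(0.50 × 85) = 66% joining.
- One standardised continuous factor, proportional odds, and binary coding 3-4 v 0-2.
- The MAQ distributions in the table.

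**Information per patient on the log odds ratio, near the null.** Ordinal: (1 − Σp³)/3, where p are the five level proportions. Binary: q(1 − q), where q is the share scoring 3-4.

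| q | MAQ 0/1/2/3/4 (%) | Σp³ | Ordinal | Binary | Ratio |
|---|---|---|---|---|---|
| 0.33 | 22/22/23/20/13 | 0.0437 | 0.3188 | 0.2211 | 0.69 |
| 0.50 | 15/15/20/27/23 | 0.0466 | 0.3178 | 0.2500 | 0.79 |

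For equal power the binary model would need 1/0.694 = 1.44 or 1/0.787 = 1.27 times as many patients.

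**Power** = Φ(ln(OR) × √(N × information) − 1.96). With N = 85 and an odds ratio of 1.75 per SD, ln(OR) = 0.5596:
- q = 0.33: binary Φ(2.426 − 1.96) = 68%; ordinal Φ(2.913 − 1.96) = 83%.
- q = 0.50: binary Φ(2.580 − 1.96) = 73%; ordinal Φ(2.909 − 1.96) = 83%.

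**Loss at a given ordinal power.** With r the ratio above and z the normal quantile of the ordinal power, binary power = Φ((z + 1.96)√r − 1.96). At 70% ordinal power and q = 0.33 this is Φ(2.484 × 0.833 − 1.96) = 54%, a loss of about 16 points. For ordinal power from 40% to 90%, the loss is 10 to 16 points at q = 0.33 and 7 to 10 points at q = 0.50.

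**Outside that range**
- Fewer patients at 3-4: the ratio falls to 0.59 at q = 0.25 and 0.51 at q = 0.20. At 80% ordinal power the losses are about 22 and 28 points.
- Very low power: N = 56, OR 1.3 gives 15.0% v 19.7% (q = 0.33) and 16.4% v 19.7% (q = 0.50).
- Power near 100%: N = 174, OR 2 gives 99.0% v 99.9% (q = 0.33).
- Only three levels (0 / 1-2 / 3-4), N = 85, OR 1.75: ordinal power is 79% with 22/45/33% and 77% with 15/35/50%. The gain over binary is then about 11 and 4 points.

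**Simulation** (300 datasets per cell, likelihood-ratio tests, slightly different assumed distributions). At 33%: 44% binary v 56% ordinal (N = 85, OR 1.5) and 63% v 79% (N = 56, OR 2). At 50%: 48% v 57% and 66% v 80%. Type I error was 3% to 7% for both models.

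**When proportional odds fails.** If the factor acts only at the 3+ cut (q = 0.33, 400 datasets per cell), the binary model is better by 5 to 19 points, for example 82% v 66% at N = 85, OR 2.

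**The case against.** The strongest reply is that nothing here is wrong. Logistic regression for non-adherence is valid, its type I error is sound, and it matches wording in the objectives that speaks of non-adherence. What sets the low-adherence group apart is a legitimate question, and a proportional-odds slope answers a somewhat different one by averaging over all cuts. If a factor matters only at the 3+ threshold, the binary model wins. This stands, and is why the binary model should be kept.

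A second reply is that the outcome coding is inferred. That also stands, but it is a well-supported inference: section 5.3.1 assigns non-adherence to the MAQ and section 5.4 holds the only two-way split.

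A third is that one-point differences on a four-item scale with a reported alpha of 0.61 carry little weight. Measurement error blurs the cut as well, so this does not favour dichotomising.

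A reader might go further and infer that this one model decides which factors are reported, or that counselling will be misdirected. The protocol does not support either. Section 9 also plans bivariate analyses, not tied to any cut, and merges the survey results with the interview themes. Although section 3.1 says Phases one and two inform the motivational interviewing, sessions are tailored to the individual (section 3.2) and held during that patient's six-week programme (section 5.2), while recruitment may last six months. A pooled regression cannot steer most of them.

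**Conclusion.** The point holds as a conditional loss of efficiency in the named model for part of a primary objective. With 33% to 50% scoring 3-4 and proportional odds roughly true, the section 5.4 cut would keep about 69% to 79% of the available information and cost about 7 to 16 power points at moderate power. Survey size, effect size, MAQ distribution and proportional odds are all assumed, because the protocol gives none of them.

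Two stronger readings are tempting. One is that some fixed loss, as high as 25 points, can be stated for this study: that size needs only about 20% to 25% scoring 3-4, below the protocol's background range. The other is that the gain vanishes only when power is already high: it is also under 5 points when power is very low.

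A separate gap in the text needs no assumption: a MAQ score of 0 has no class, so the binary outcome is incompletely defined.

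**What to change.** In section 9, Phase one:

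- Make proportional-odds (ordinal logistic) regression on the MAQ score (0-4) the main model for associated factors, reported as odds ratios with 95% confidence intervals.
- State in advance how sparse levels will be collapsed, for example to the three bands of section 5.3.1 (0 / 1-2 / 3-4). Collapsing gives back part of the gain, as shown above.
- Keep the binary logistic model (3-4 v 0-2, with a score of 0 explicitly placed) as a secondary analysis and as a check on proportional odds.
- Leave the eligibility cut in section 5.4 unchanged.

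The cost is a short change of text. It needs no new data or patients. The downside is reliance on approximate proportional odds in the main model, which the retained binary analysis helps to check.

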#### Sample size calculation:

- With alpha = 0.05 (2sided), power= 0.80 (beta= 0.20).
- With consecutive sampling and allowing for 50% loss to follow-up.
- A sample size of 28 participants for both groups will be recruited (Ma et al. 2014).

**Recruitment and screening**: Patients referred to Cardiac Rehabilitation at POWH will be screened by the Clinical Nurse Consultant (CNC) as they attend their first session. For Phases One and Two, eligible patients will:

- Have an established diagnosis of cardiac disease by their physician;
- Will have been prescribed at least one cardio-protective medication at least 7 days prior to recruitment;
- They must have primary responsibility for taking their medication themselves (i.e. whilst a carer may play a role in supporting or promoting medication taking, they should not be identified as being accountable for ensuring the patient's adherence to their medication schedule);
- Patients must not be clinically judged as affected by cognitive impairment and must be able to speak, read and understand English, own a personal mobile phone, and be able to receive and reply to phone calls and text messages.

All patients recruited will complete a paper-based survey (phase one) and a brief face to face interview (phase two).

For the Pilot Trial Phase:

Participants identified as 'non-adherent' to at least one of their cardiac medications, based on the
result of exploratory phases of the study (survey and interview), will be invited to participate in
the final pilot randomised trial phase.

Patients recruited to the pilot trial phase will be randomly allocated to either an intervention or control arm.

**Intervention:** Participants in the intervention group will receive usual care plus behavioural counselling about medication adherence using motivational interviewing (MINT) techniques and text message reminders.

**Control group**: will receive the usual cardiac rehabilitation program.

**Analysis plan:** Phase one: Descriptive statistics; Phase two: thematic analysis; Pilot trial Phase: descriptive statistics and inferential data analysis.

**Duration of the study:** The total duration of the study will be 12 months (six months for recruitment and six months participation for each participant recruited).

Version 2: 20/05/2016 ------ Page 4 of 42

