#### 3.3. NUMBER OF PARTICIPANTS

The researcher will sample of a cohort participants referred to cardiac rehabilitation for phases one and two until adequate numbers have been recruited for pilot trial phase. To calculate the sample size for the study, the researcher used values for the means (M) and standard deviation (SD) based on data from Ma et al. (2014) using the following formula:

Cohen's  $d = M1 - M2 / \sigma$  pooled, where  $\sigma$  pooled =  $\sqrt{(\sigma 12 + \sigma 22) / 2}$ 

M1= means for group  $1 = 29.72\pm3.46$ 

M2= means for group  $2 = 25.30 \pm 3.11$ 

Version 2: 20/05/2016 ----- Page 10 of 42

The resultant value for 2 sided test for alpha = 0.05, with power = 0.80, is a sample size of 9 for each group. Based on the results of the sample size calculation formula, 9 participants with complete data in each group will be required to detect a difference in the means of 4.42 points for the primary outcome at 6 months, assuming a common standard deviation of 3.285, with a power of  $\beta = 80\%$  and a two-sided  $\alpha$  value of 0.05. Assuming up to 50% attrition, a total of 28 participants will be recruited for pilot trial phase.

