The Medication Adherence Self-Efficacy Scale-Revised (MASES-R) consists of 13 items that evaluate an individual's judgment of their ability to adhere to prescribed medications under a variety of challenging situations. Twelve of the items ask about patient confidence in taking medications in specific situations (e.g. busy at home, no symptoms, traveling), and one item addresses confidence in ability to make medication adherence as part of daily routine. Each item is scored on a four point scale, ranging from: 0= Not at all sure, 1= A little sure, 2= Fairly sure, and 3= Extremely sure. A single scale score is presented, the mean of all item scores. Higher scores on the scale indicate higher confidence.

The **Medication Specific Social Support** (MSSS) is an 8-item survey of medication-specific social support to identify how often others may have helped patients with their therapy, with scored for each item ranging from 0 (never) to 4 (very often). A single mean score is presented of medication-specific index of support.

These instruments have demonstrated rigor; see Table 1.

Version 2: 20/05/2016 ----- Page 16 of 42

Table 5: The reliability and validity of the selected study instruments

Concept	Name of Questionnaire	Number of Items	Validity Test	Reliability Test Score
Medication Adherence behaviours & barriers	Medication Adherence Questionnaire (MAQ)	Four-item questionnaire measure medication adherence behaviour specifically, barriers such as; forgetfulness and carelessness, & adverse effects & efficacy	Validated in patients with hypertension, dyslipidaemia, heart failure, and CAD	Cronbach's α= 0.61
Medication Adherence Behaviour (Self- Regulation)	Adherence to Refills and Medications Scale (ARMS)	12-item scale.     The first 8-item medication taking subscale assess correct self-administer prescribed regimen ability.     The next 4-item prescription refill subscale assesses a patient's ability to refill medications on schedule	Validated in patients with CAD & other chronic diseases	Cronbach's α = 0.81
Medication taking beliefs	Belief about Medicine Questionnaire (BaMQ)	●8-item short version.  ● The 4-BaMQ subscales are containing two items each includes: General Harm; General Overuse; Specific Necessity; & Specific Concerns on a five point Likert scale.	BaMQ significantly correlated with other adherence scales: MAQ, Morisky Medication Adherence Scale (MMAQ), & medication adherence rating scale (MARS-5)	Cronbach's α = 0.70

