#### 5.6. RANDOMISATION PROCEDURE: PILOT TRIAL PHASE ONLY

In pilot trial phase participants will be randomly allocated to receive either multifaceted intervention comprising current standard care plus motivational interviewing (MINT) follow by text messages or current standard care alone. Participants will be randomised after they have consented to participate in the trial phase, so that the decision to participate has no bearing on which arm of the trial they are allocated to. A random sequence will be generated by computerised random number generator and using permutated blocks in order to assure equal numbers in each arm, balanced at set intervals at 1:1 ratio.

Version 2: 20/05/2016 ----- Page 19 of 42

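### Within-arm paired t-tests on the MAQ will pick up regression to the mean, and no baseline-adjusted between-arm analysis is specified

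*Protocol*

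**What the plan says.** Section 9 (pilot trial phase) names two tests for the questionnaire scores. Between arms: "The independent samples t-test will be used to compare the mean medication adherence questionnaire scores". Within arms: "Paired samples t-test analysis will be used to test within groups differences on medication adherence questionnaire scores". Both cover five scales: MSSS, MAQ, ARMS, BaMQ and MASES-R. The primary outcome in sections 2.2 and 9 combines adherence status at six months with change since baseline. No baseline adjustment is mentioned, and the first sentence does not say whether the means compared are six-month scores or changes.

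Three other places matter:

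- Section 5.3.1 scores MAQ from 0 to 4, higher being worse. Its instrument table gives "Cronbach's α= 0.61" for MAQ.
- Section 5.4 classes a total of 3-4 as non-adherent and invites those patients to the trial. Section 4.1, item 7, instead asks for at least one non-adherence factor, judged from the questionnaire and the interview.
- The schedule in section 5.2 has the survey only at enrolment and at the six-month contact, so the score that selects a patient is also that patient's baseline.

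**The concern.** Patients chosen because one imperfectly reliable measurement was extreme will score less extremely on average when measured again, treated or not. A paired t-test within an arm tests that fall together with any real change and cannot separate them. The hypothesis in section 1.2 is comparative (intervention plus standard care against standard care alone), and a within-arm test does not address it.

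Five scales in two arms give 5 × 2 = 10 within-arm tests against five between-arm tests. The within-arm tests are also the only ones tied expressly to before-after differences, although change is part of the primary outcome. At stake is a pilot report in which significant improvement within the intervention arm is read as a sign of efficacy when it comes from the entry rule. Separately, every scale has a baseline value, but the plan names no between-arm analysis that adjusts for it.

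**Working it through.** **1. Number of patients.** The plan's own figure reproduces: n = 2(1.96 + 0.842)² × 3.285² / 4.42² = 169.448 / 19.5364 = 8.67, so 9 completers per group. Section 3.3 adds: "Assuming up to 50% attrition, a total of 28 participants will be recruited for pilot trial phase". That is 14 per arm randomised. The checks below use 9 (the target for complete data) and 14 (no loss).

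**2. Expected fall, normal model.** If a share p of patients is selected from the upper tail and the retest correlation is r, the expected fall is (1 − r) × φ(c)/p population SDs, where c is the cut-off. The protocol gives neither p nor r; alpha of 0.61 is internal consistency, not retest reliability. For p = 0.20 the fall is 0.70 SD at r = 0.5 and 0.42 SD at r = 0.7. For p = 0.33 it is 0.55 and 0.33 SD.

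**3. Simulation on the MAQ scale.** Assumptions: four yes/no items driven by one trait, alpha 0.59-0.62, selection on a total of 3-4, no intervention effect, no true mean change, and 20,000 trials per size. Item yes-rates are 0.5, 0.4, 0.25, 0.2 (set A, about 20% selected) or 0.6, 0.5, 0.4, 0.35 (set B, about 34% selected). The last two columns give the share of arms significant for improvement, nominally 2.5% in that direction.

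| Set | Retest r | Mean fall | SD of change | No longer 3-4 | Paired test, n = 9 | Paired test, n = 14 |
|---|---|---|---|---|---|---|
| A | 0.60 | 0.77 | 1.09 | 45% | 43% | 68% |
| A | 0.47 | 1.03 | 1.21 | 54% | 58% | 85% |
| B | 0.62 | 0.59 | 1.06 | 35% | 27% | 48% |
| B | 0.49 | 0.80 | 1.19 | 42% | 39% | 64% |

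Hand check of the first row at n = 9: 0.77 / (1.09/√9) = 2.12 against a critical value of 2.306, consistent with rejection a little under half the time. A further simulation with alpha 0.66-0.68 gives falls of 0.5-1.1 points and rejection in 18-55% (n = 9) and 34-83% (n = 14). Together these support the rounded ranges of 20-60% and 35-85%. At a retest correlation of 0.35-0.36 the fall reaches 1.00-1.28 points and rejection 50-73% and 78-94%.

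**4. Discordant arms.** With no effect, the chance that the intervention arm is significant and the control arm is not is p(1 − p), p now being the rejection rate. At n = 9 this runs from 0.27 × 0.73 = 0.20 to 0.43 × 0.57 = 0.25. At n = 14 it runs from 0.85 × 0.15 = 0.13 to 0.48 × 0.52 = 0.25.

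**5. Between-arm test.** In the four tabulated settings the independent t-test rejects in 4.7-5.6% of trials, on six-month scores or on changes.

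**6. Looser entry rule.** With entry at MAQ 1 or more, one way to represent section 4.1, item 7, the fall is 0.17-0.40 points and the paired test rejects in about 7-20% of arms.

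**7. Gain from baseline adjustment.** Relative to an unadjusted six-month comparison, ANCOVA leaves a fraction 1 − r² of the variance. Selection on 3-4 restricts baseline MAQ, and the simulated within-trial correlation is only 0.14-0.28. The variance removed is 0.14² = 2% to 0.28² = 8%; roughly 2-10% is a fair range. For the other scales r is not given: r = 0.2 removes 4%, r = 0.5 removes 25%.

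**The case against.** The strongest reply is that the trial's comparison is sound. Patients are randomised, the analysis is by intention to treat, a between-arm test is named, and regression to the mean acts on both arms alike. That stands: step 5 shows a false-positive rate near 5%. A reader might infer that the trial's main result is biased, or that the investigators intend to argue from significance in one arm and not the other. Nothing in the protocol supports either reading. What remains is that inferential tests are planned which do not answer the study's question.

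Four further replies have force:

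- *Baseline ignored?* A reader might say so of the between-arm test. The protocol does not establish it: change is part of the primary outcome, and the t-test could be run on changes. Nor does the usual warning that change scores are noisier when r is below 0.5 apply to MAQ. Its factor 2(1 − r) assumes equal variances, and selection shrinks the baseline variance; the simulated ratio of change variance to six-month variance is 0.92-1.00.
- *Large precision gain?* Residual variances of 0.75 and 0.64 (r = 0.5 and 0.6) would be worth 33% and 56% more patients. The protocol gives no r, and step 7 rules out such a gain for MAQ.
- *Scope.* Selection acts directly on MAQ and reaches the other four scales only through their correlation with it. The planned difference of 4.42 points exceeds MAQ's 0-4 range, so the artefact is not quantified for the scale behind the sample size.
- *Entry rule.* Section 4.1 is looser than section 5.4, and section 9 lets the participant settle contradictions between survey and interview. Under looser entry the problem is much smaller (step 6), though still above the nominal level.

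**Conclusion.** The point holds in limited form. If entry follows section 5.4, paired t-tests on MAQ will often be significant with no intervention effect: about 20-60% of arms at 9 completers and 35-85% at 14, with a fall of about 0.5-1.1 points. This rests on no true mean change over six months and a retest correlation of about 0.5-0.7, neither of which the protocol supplies. These tests should carry no weight as evidence of efficacy.

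The between-arm t-test is valid. Its defects are that the score it uses is ambiguous and that no baseline-adjusted analysis is specified. Lack of adjustment costs some precision and leaves chance baseline imbalance uncorrected in a trial of 14 per arm. The precision loss is small for MAQ and unknown, possibly larger, for ARMS and the other scales. Because section 9 names these tests, this is a choice fixed badly rather than detail left for later. It should be changed.

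**What to change.** In section 9, replace the two t-test sentences. For each scale, make the efficacy analysis a between-arm ANCOVA of the six-month score on arm and that scale's baseline score, reported as an adjusted difference with a 95% CI. This also settles which score is compared. Report within-arm change as means and SDs, without tests. State that MAQ is expected to fall in both arms because of the entry criterion.

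Reconcile the trial-entry rules in sections 4.1 (item 7) and 5.4, since the size of the artefact depends on which applies.

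The cost is wording and one degree of freedom per analysis; the scores are already collected. The change does not cover the six-month adherent/non-adherent outcome. A mixed model should not be offered as a way to let all 28 contribute: with a single follow-up, patients lost before six months supply only baseline data and add little.
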